8.2.1. Physical Examinations

Focused physical examinations including skin assessment will be completed prior to treatment, and at 2, 3, 4, 7, 10, 13, and 14 months. Focused examinations are generally limited to the body systems or regions based on participant's self-assessment and AE reporting. Any new complaints, symptoms reported by participants or adverse events noted by providers should guide the need and extent of physical examination.

8.2.2. Vital Signs

Vital signs are to be assessed per standard of care or as warranted by AEs.

8.2.3. Electrocardiograms

A 12-lead ECG will be conducted prior to treatment to assess for QT prolongation, if not available from pre-operative evaluation. During the collection of ECGs, participants should be in a quiet setting without distractions (eg, television, cell phones). Participants should rest in a supine position for at least 5 minutes before ECG collection and should refrain from talking or moving arms or legs. If blood sampling or vital sign measurement is scheduled for the same time point as ECG recording, the procedures should be performed in the following order: ECG(s), vital signs, blood draw.

8.2.4. Clinical Safety Laboratory Assessments

Blood samples will be collected as noted in Section 10.2, Appendix 2, Clinical Laboratory Tests. The investigator must review the laboratory results, document this review, and record any clinically relevant changes occurring during the study in the AE section of the eCRF. The laboratory reports must be filed with the source documents. The only study-specified laboratory assessments are PSA and testosterone.

8.3. Adverse Events and Serious Adverse Events

Timely, accurate, and complete reporting and analysis of safety information from clinical studies are crucial for the protection of participants, investigators, and the sponsor, and are mandated by regulatory agencies worldwide. The sponsor has established Standard Operating Procedures in conformity with regulatory requirements worldwide to ensure appropriate reporting of safety

information; all clinical studies conducted by the sponsor or its affiliates will be conducted in accordance with those procedures.

Adverse events will be reported by the participant (or, when appropriate, by a caregiver, surrogate, or the participant's legally acceptable representative) for the duration of the study.

For further details on AEs and SAEs (Definitions and Classifications; Attribution Definitions; Severity Criteria; Special Reporting Situations; Procedures) as well as product quality complaints, refer to Section 10.4, Appendix 4, Adverse Events, Serious Adverse Events, Product Quality Complaints, and Other Safety Reporting: Definitions and Procedures for Recording, Evaluating, Follow-up, and Reporting.

8.3.1. Time Period and Frequency for Collecting Adverse Event and Serious Adverse Event Information

All Adverse Events

Monitoring of AEs will be performed at 1, 2, 3, 4, 7, 10, 13, 14 months, at each follow-up visit, and during phone calls with the participants. All AEs and special reporting situations, whether serious or non-serious, will be reported from the time after the participant receives the first dose of apalutamide until completion of the participant's last study-related procedure, which may include contact for follow-up of safety. Serious adverse events, including those spontaneously reported to the investigator within 30 days after the last dose of study intervention, must be reported using the SAE Form. The sponsor will evaluate any safety information that is spontaneously reported by an investigator beyond the time frame specified in the protocol.

Serious Adverse Events

All SAEs occurring during the study must be reported to the appropriate sponsor contact person by study-site personnel within 24 hours of their knowledge of the event.

Information regarding SAEs will be transmitted to the sponsor using the SAE Form, which must be completed and signed by a physician from the study site, and transmitted to the sponsor within 24 hours. The initial and follow-up reports of an SAE should be emailed to the to the appropriate sponsor contact person by study-site personnel.

8.3.2. Method of Detecting Adverse Events and Serious Adverse Events

Care will be taken not to introduce bias when detecting AEs or SAEs. Open-ended and nonleading verbal questioning of the participant is the preferred method to inquire about AE occurrence.

Participants who are not able to respond verbally, may be asked to write a brief description of how they have been feeling.

8.3.3. Follow-up of Adverse Events and Serious Adverse Events

Adverse events, including pregnancy, will be followed by the investigator as specified in Section 10.4, Appendix 4 Adverse Events, Serious Adverse Events, Product Quality Complaints,

and Other Safety Reporting: Definitions and Procedures for Recording, Evaluating, Follow-up, and Reporting.

8.3.4. Regulatory Reporting Requirements for Serious Adverse Events

The sponsor assumes responsibility for appropriate reporting of AE to the regulatory authorities. The sponsor will also report to the investigator (and the head of the investigational institute where required) all suspected unexpected serious adverse reactions (SUSARs). The investigator (or sponsor where required) must report SUSARs to the appropriate Independent Ethics Committee/Institutional Review Board (IEC/IRB) that approved the protocol unless otherwise required and documented by the IEC/IRB.

The plan for monitoring and analyzing the anticipated events is specified in the IB.

The sponsor assumes responsibility for appropriate reporting of the listed anticipated events according to the United States requirements.

8.3.5. Pregnancy

All initial reports of pregnancy in partners of male participants must be reported to the sponsor by the study-site personnel within 24 hours of their knowledge of the event using the appropriate pregnancy notification form. Abnormal pregnancy outcomes (eg, spontaneous abortion, fetal death, stillbirth, congenital anomalies, ectopic pregnancy) are considered SAEs and must be reported using the SAE Form. Follow-up information regarding the outcome of the pregnancy and any postnatal sequelae in the infant will be required.

8.3.6. Cardiovascular and Death Events

Ischemic cardiovascular events, including events leading to death, occurred in patients receiving apalutamide. Monitor for signs and symptoms of ischemic heart disease. Optimize management of cardiovascular risk factors, such as hypertension, diabetes, or dyslipidemia. Consider discontinuation of apalutamide for Grade 3 and 4 events.

8.3.7. Disease-Related Events and Disease-Related Outcomes not Qualifying as Adverse Events or Serious Adverse Events

All events that meet the definition of an SAE will be reported as SAEs, regardless of whether they are protocol-specific assessments.

Disease progression should not be recorded as an AE or SAE term; instead, signs and symptoms of clinical sequelae resulting from disease progression/lack of efficacy will be reported if they fulfil the SAE definition (refer to Adverse Event Definitions and Classifications in Section 10.4, Appendix 4, Adverse Events, Serious Adverse Events, Product Quality Complaints, and Other Safety Reporting: Definitions and Procedures for Recording, Evaluating, Follow-up, and Reporting). Expected progression of disease should not be considered an AE (or SAE). However, if determined by the investigator to be more likely related to the study intervention than the underlying disease, the clinical signs or symptoms of progression and the possibility that the study

intervention is enhancing disease progression, should be reported per the usual reporting requirements.

8.3.8. Adverse Events of Special Interest

For apalutamide, there are no non-serious AEs of special interest identified.

Rash is an AE of special interest to be assessed by CTCAE criteria and following the specific rash management plan in Appendix 9, Recommendations for Management of Drug related Rash.

8.4. Pharmacokinetics (Not Applicable)

8.5. Genetics

Genetics will be evaluated by DNA repair deficient (DRD) germline testing using whole blood sample.

8.6. Biomarkers

Biomarker samples may be collected as outlined in the SoA. Biomarker analysis is planned to retrospectively evaluate risk scores and other genomic markers and correlate with participants' response to treatment and explore HRD status and efficacy of apalutamide in this subpopulation. To address these objectives, tumor tissue will be collected and sent to sponsor's laboratory partner along with a copy of the full histopathology report of the specimen. Biopsy tissue is required for risk scores (Prolaris) and is preferred for HRD testing Also, whole blood and plasma samples may be collected at baseline, 12 months or end of treatment, and at 24 months or progression (whichever comes first).

Stopping Analysis

Biomarker analyses are dependent upon the availability of appropriate biomarker assays and clinical response rates. Biomarker analysis may be deferred or not performed, if during or at the end of the study, it becomes clear that the analysis will not have sufficient scientific value for biomarker evaluation, or if there are not enough samples or responders to allow for adequate biomarker evaluation. In the event the study is terminated early or shows poor clinical efficacy, completion of biomarker assessments is based on justification and intended utility of the data.

Additional Collections

If it is determined at any time before study completion that additional material is needed from a formalin-fixed, paraffin-embedded tumor sample for the successful completion of the protocol specified analyses, the sponsor may request that additional material be retrieved from existing samples. Also, based on emerging scientific evidence, the sponsor may request additional material from previously collected tumor samples during or after study completion for a retrospective analysis. In this case, such analyses would be specific to research related to the study intervention(s) or diseases being investigated.

8.7. Immunogenicity Assessments (Not Applicable)

8.8. Health Economics (Not Applicable)

9. STATISTICAL CONSIDERATIONS

Statistical analysis will be done by the sponsor or under the authority of the sponsor. A general description of the statistical methods to be used to analyze the efficacy and safety data is outlined below. Specific details will be provided in the Statistical Analysis Plan.

9.1. Statistical Hypotheses

The primary hypothesis of this study is that adjuvant treatment with apalutamide and ADT will improve the BCR-free rate at 24 months in the treatment-naïve, non-metastatic prostate cancer population who are at high risk for the development of metastases compared to historical data without adjuvant treatment (76%).¹⁴

9.2. Sample Size Determination

It is assumed that BCR-free rate follows an exponential distribution with a constant hazard rate. It is estimated that approximately 94 participants accrued over approximately 1 year, treated for 12 months and followed for an additional 12 months would be required to provide at least 80% power in detecting a 10% absolute increase in BCR-free rate at 24 months of 76% to 86% at a 1-tailed significance level of 0.05. The null hypothesis of 76% BCR-free rate at 24 months for the historical data of no adjuvant treatment is an estimate based on published data.¹⁴ Sample size was calculated using PASS 15 (Power Analysis and Sample Size Software [2017]).²⁰

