9.4.1. General Considerations

Primary endpoint test of hypothesis will be performed at 1-sided significant level 0.05; a 2-sided alpha level of 0.10 will be used to provide all confidence intervals.

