9.4.2. Primary Endpoint

Time to BCR (ie, PSA >0.2 ng/mL) will be analyzed using Kaplan-Meier method. The BCR -free rate at 24 months will be estimated with the 90% confidence interval. Null hypothesis of BCR free- rate of 76% will be rejected if the lower limit of the 90% confidence interval exceeds 76%. Participants who do not have any occurrence of PSA >0.2 ng/mL, will be considered as censored at their last time of PSA measurement.

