1.2. Study Design

This is a single-arm, open-label, multi-center study of apalutamide and ADT in 96 participants with high risk localized prostate cancer who are treatment naïve, documented to have no evidence of metastatic disease prior to study entry, who are no more than 60 days post radical prostatectomy (RP), whose prostate-specific antigen (PSA) is ≤ 0.2 ng/mL at study entry and who have recovered from surgery, per the clinical judgement of the investigator.

There will be one intervention group receiving apalutamide with ADT of investigator's choice (3-month depot preferred) for 12 months. Treatment with apalutamide and ADT will start following screening and completion of RP and no later than postoperative Day 60. Approximately 30 days post-treatment, a safety follow-up examination will be completed (end of treatment visit). There will be a follow-up period during which serum PSA and testosterone levels will be measured and clinical status monitored every 6 months after the completion of treatment until the end of the study (EOS). The EOS is defined as the date of last participant's enrolment + 24 months or discontinuation of all study participants from the study, whichever occurs first. Study enrollment is defined as the day when the participant receives the first dose of apalutamide after having met all pre-screening criteria.

A diagram of the study design is provided below.

Key: ADT=androgen deprivation therapy; EOS=end of study; N=number of participants; post-op=postoperative; PSA=prostate-specific antigen; RP=radical prostatectomy.

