3. SAMPLE SIZE DETERMINATION

It is assumed that BCR-free rate follows an exponential distribution with a constant hazard rate. It is estimated that approximately 94 participants accrued over approximately 1 year, treated for 12 months and followed for an additional 12 months would be required to provide at least 80% power in detecting a 10% absolute increase in BCR-free rate at 24 months of 76%¹ to 86% at a 1-tailed significance level of 0.05. Sample size was calculated using PASS 15 (Power Analysis and Sample Size Software $[2017]^2$.

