5. STATISTICAL ANALYSES

5.1. General Considerations

Study Day will be calculated in reference to the date of first dose of study drug (apalutamide). Positive study days will count forward from Study Day 1. Study Day -1 will be the day before Study Day 1, and all subsequent negative study days will be measured backward from Study Day -1. There will be no Study Day 0.

The first dose starts on Day 1 of Cycle 1.

Unless otherwise specified, baseline value is defined as the closest measurement prior to the first dose of study drug. Change from baseline will be defined as (post-baseline value – baseline value).

Treatment Duration will be calculated as the duration of time from the date of the first dose of study drug (apalutamide) to the date of last dose of the study drug, i.e., date of last dose – date of first dose + 1.

Time to Event endpoints will be calculated as the number of days from the start of the study drug to the date of the event of interest, i.e., date of event of interest – date of first dose + 1. Time to event or duration of event endpoints will be based on the actual date of the event, not visit number or visit label. Confidence intervals of survival function at specific time point will be calculated using Kaplan-Meier method. In case no events have occurred by the given time point, a conservative approach will be used by assuming one event at the time point among subjects still at risk.

Continuous/numerical variables will be summarized using mean, standard deviation (SD), median, minimum, and maximum. Categorical variables will be summarized using count and percentage. In general, means and other measures of central tendency will be displayed with one more decimal digit than collected, and standard deviations and other measures of variability will be displayed with two decimal digits more than collected. For frequency counts of categorical variables, categories for which the counts are zero will be displayed for the sake of completeness. For example, if no subject discontinued due to "withdrawal of consent", this reason would still be included in the table but with a count of 0.

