5.3.3. Analysis Methods

The analysis of time to BCR will be performed at the end of study which is defined as the date of last participant's enrolment + 24 months or discontinuation of all study participants from the study, whichever occurs first. The distribution of time to BCR will be estimated using the Kaplan-Meier (KM) method. Median BCR-free time along with 90% confidence interval will be reported with Kaplan-Meier curve. The null hypothesis will be rejected if lower limit of the 90% confidence interval of KM estimate of BCR-free rate at 24 months is > 76%.

Time to unconfirmed BCR will be evaluated using same methodology as sensitivity analysis.

Modified ITT analysis set will be used for the analysis. Subjects with no evidence of BCR will be censored based on following rule:

- If the subject does not have baseline PSA measurement, the subject will be censored on the date of enrollment (Study Day 1)
- If the subject does not have confirmed PSA >= 0.2 ng/mL, the subject will be censored on the date of the last PSA measurement
- If the subject receives a protocol specified prohibited or restricted therapy, PSA measurements on or after such therapy will not be included in the analysis

These censoring rules will be applied appropriately to all intercurrent events in the trial as defined in Table 1. The details are as specified in Table 2.

| Intercurrent Event (IE) / EOS | Censoring (if no event, before the IE) | Assumption |
|--|---|---|
| IE: Study withdrawal due to any reason, any time during the study | PSA value censored at study withdrawal | Non-informative censoring as per censoring rule |
| IE: Use of restricted and prohibited concomitant therapy any time during the study | PSA value censored at the last PSA assessment prior to the time of the start of restricted and prohibited concomitant therapy | Non-informative censoring as per censoring rule |

Table 2: Censoring Rules to be used for intercurrent events

| IE: Death | PSA value censored at the last PSA assessment prior to the time of death | Non-informative censoring as per censoring rule |
|--------------|--|---|
| End of study | (Administratively) censored at the last PSA assessment prior to the end of the study | Non-informative censoring as per censoring rule |

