6.2. Appendix 2 Changes to Protocol-Planned Analyses

To be updated as necessary and will be finalized before data base lock.

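### The primary decision limit is not defined, and no common Kaplan-Meier limit gives the stated 80% power at one-sided 5% with 94 participants

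*Protocol*

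**What the plan says.** - **Sizing.** Protocol 9.2 assumes exponential times to biochemical recurrence (BCR) and says about 94 participants will "provide at least 80% power in detecting a 10% absolute increase in BCR-free rate at 24 months of 76% to 86" percent, one-tailed at 0.05. SAP 3 repeats that 94 "would be required to provide at least 80% power in detecting a 10% absolute increase in BCR-free rate at 24 months". Both cite PASS 15; neither names the procedure. SAP 1.2 gives a different number: "multi-center study of apalutamide and ADT in 96 participants".
- **Test level.** Protocol 9.4.1: "Primary endpoint test of hypothesis will be performed at 1-sided significant level 0.05".
- **Decision rule.** Protocol 9.4.2: the null "will be rejected if the lower limit of the 90% confidence interval exceeds 76" percent. SAP 5.3.3: "rejected if lower limit of the 90% confidence interval of KM estimate of BCR-free rate at 24 months is > 76" percent.
- **Interval.** SAP 5.1 is the only place that says how the interval is built: "Confidence intervals of survival function at specific time point will be calculated using Kaplan-Meier method". It adds a rule for the case of no events by the time point. Neither document mentions plain (linear), log, log-log, arcsine or exact limits.
- **Changes.** SAP Appendix 2, on changes to protocol-planned analyses, reads: "To be updated as necessary and will be finalized before data base lock".

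**The concern.** Kaplan-Meier names an estimator, not an interval. Several standard limits can be built on it, and they differ enough at this sample size to move the cut-off by one participant. That one participant separates a test that exceeds its declared 5% error from one that falls short of its declared 80% power.

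This is a single-arm trial against a fixed historical rate, so this comparison is its only formal error control. If the limit type is still open when the data are seen, the more favourable one could be chosen. Version 2.0 of the SAP revised SAP 5.1 on exactly this subject but settled only the no-event case. About 13 events (94 × 0.14) are expected at an 86% rate and about 23 (94 × 0.24) at 76%, so that rule does not help.

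**Working it through.** **Inputs.** n = 94, null rate 0.76, alternative 0.86, one-sided alpha 0.05, power at least 0.80 (Protocol 9.2, SAP 3). Success if the lower two-sided 90% limit exceeds 0.76 (Protocol 9.4.2, SAP 5.3.3), so z = 1.645. Dropout rates are assumptions; the documents give none.

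**1. The plan's own figure.** Single-arm arcsine approximation:

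h = 2(asin √0.86 − asin √0.76) = 0.25695

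n = ((1.645 + 0.8416)/h)² = 93.64, rounded up to 94

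power at 94 = Φ(h√94 − 1.645) = 80.1%

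So 94 reproduces. The method is inferred, because the PASS procedure is not named.

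**2. The rule as written, complete follow-up.** With no censoring before 24 months the Kaplan-Meier estimate is s = x/n and the Greenwood standard error is se = √(s(1−s)/n). The lower limits are:

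- plain: s − z·se
- log: s·exp(−z·se/s)
- arcsine: sin²(asin √s − z/(2√n))
- log-log: s^exp(z·se/(s·|ln s|))
- exact (Clopper-Pearson): 5th percentile of Beta(x, n−x+1)

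At 78/94, s = 0.8298 and se = 0.03876:

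| Limit | at 78/94 | Result at 78 | Needs |
|---|---|---|---|
| plain | 0.7660 | success | 78 |
| log | 0.7684 | success | 78 |
| arcsine | 0.7616 | success | 78 |
| log-log | 0.7545 | failure | 79 (0.7665) |
| exact | 0.7530 | failure | 79 (0.7650) |

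Binomial tails at n = 94:

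| Cut-off | alpha (true 76%) | power (true 86%) |
|---|---|---|
| 78 or more | 6.78% | 84.02% |
| 79 or more | 3.97% | 76.24% |

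The two cut-offs are adjacent, so no cut-off at n = 94 has both alpha at or below 5% and power at or above 80%. The chance of landing exactly on 78, where the limit type decides the verdict, is 7.77% at 86% and 2.81% at 76%.

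**3. With dropout.** Kaplan-Meier simulation, n = 94, exponential BCR times, independent exponential dropout censored, Greenwood variance, 200,000 runs per setting. Entries are alpha / power in %:

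| Dropout by 24 months (assumed) | log-log | arcsine | plain | log |
|---|---|---|---|---|
| 2% | 4.4 / 77.1 | 5.7 / 80.7 | 7.4 / 84.6 | 7.5 / 85.0 |
| 5% | 4.2 / 75.9 | 5.3 / 79.6 | 7.0 / 83.4 | 7.8 / 85.1 |
| 10% | 4.1 / 73.8 | 5.8 / 79.5 | 6.8 / 82.0 | 7.6 / 83.6 |
| 15% | 4.1 / 72.9 | 5.8 / 78.3 | 7.0 / 81.4 | 7.8 / 82.8 |

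No cell meets both figures.

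**4. The 96 in SAP 1.2, complete follow-up.**

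| Limit | Needs | alpha | power |
|---|---|---|---|
| log-log, exact | 81/96 | 3.15% | 73.5% |
| plain, arcsine | 80/96 | 5.49% | 81.8% |
| log | 79/96 | 8.97% | 88.2% |

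None meets both. The limit type decides the verdict at 79 or 80 of 96: probability 14.7% at 86% and 5.8% at 76%. The same dropout simulation at 96 also finds no limit type that meets both.

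**The case against.** **This compares nominal with attained properties.** A 90% interval is a nominal one-sided 5% procedure, 94 is described as approximate, and discreteness is routine. It is also true that no limit type can make the sentence true at exactly 94, and that arcsine limits with 2% dropout come close (80.7% at 5.7%). All of that stands. It does not excuse leaving the primary test undefined, and a 6.8% error rate is not what Protocol 9.4.1 declares.

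**The figures hold at one n only.** The efficacy set is modified intent-to-treat and may be smaller than 94. Attained values form a sawtooth: log-log gives 4.98% / 78.9% at 92, 3.97% / 76.2% at 94 and 4.93% / 80.6% at 97, where arcsine, log-log and exact limits coincide and meet both targets. This is fair, and the restated power should be tied to its n. But 94 is the number the documents use for their claim.

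**Visit timing could matter more.** The Schedule of Activities labels one visit both Month 24 and Cycle 24 Day 1. With 28-day cycles the latter is day 645 (23 × 28 + 1). If BCR status were in effect read then, the exponential model gives true rates of 78.5% and 87.5%, and the 79/94 rule would have about 11.5% alpha and 88% power. That is a separate issue resting on one reading of the label; it does not settle which limit applies.

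**Log-log is a choice, and a costly one for power.** It has the lowest power of the Kaplan-Meier limits in the dropout table. It is also the only one there that keeps alpha below 5%.

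**Conclusion.** The concern holds. The sample size calculation is sound as an approximation, but the pre-specified test does not deliver what is claimed for it. At n = 94 with complete follow-up it has either 76.2% power at 4.0% alpha or 84.0% at 6.8%, and nothing in the plan says which. These figures are exact given complete 24-month follow-up. Under the plan's exponential model with an assumed 2–15% dropout, log-log power is about 73–77% at 4.1–4.4% alpha, and arcsine, plain and log limits all exceed 5%. The verdict is affected only in a narrow band, but that band lies on the primary endpoint.

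**What to change.** 1. In SAP 5.1 and 5.3.3, name the log-log 90% Kaplan-Meier interval as the decision interval. At 94 it holds alpha at about 4%. At other n it can slightly exceed 5% (5.02% at 87; 5.33% at 106), so report the attained alpha at the analysed n.
2. Restate the power in SAP 3, and in Protocol 9.2 to match: n = 94 gives about 76% power at an actual one-sided alpha of about 4% with complete 24-month follow-up, and about 73–76% if an assumed 5–15% are censored by dropout. Reconcile the 96 in SAP 1.2 with 94.
3. Record the change in SAP Appendix 2 before database lock.

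A separate reporting correction: SAP 5.3.2.4 gives a 95% interval for the same 24-month rate that SAP 5.3.3 judges on 90%. Change it to 90%.

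**Cost.** Wording only, with no added enrolment or data. The SAP edits are simple. Changing Protocol 9.2 needs a formal amendment under Protocol 10.3.1, so if none is otherwise due, the SAP edits are the essential part. The stated power becomes slightly less favourable.
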